17.2 Analyses

All randomized patients, eligible and who started the induction treatment will be included in the analysis, according to the intention to treat.

Those patients who are not in CR within 2 weeks after induction cycle I will be considered as treatment failures.

The estimated CR rate after induction cycles 1 and 2 along with the 95% CI interval will be presented for each treatment arm.

The estimated severe toxicity rate (i.e. any side effect or infection of CTCAE grade 4) along with the 95% CI interval will be presented for each treatment arm.

The actuarial curves for EFS, DFS and OS will be computed using the Kaplan-Meier method and 95% CIs will be constructed.

Actuarial probabilities of relapse after CR or death in CR with corresponding standard errors will be calculated using the competing risk method.

In addition the analysis of toxicity will be done tabulation of the incidence of side effects and infections with CTCAE grade 2 or more (appendix D).

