This is a multicenter randomized phase II study. Relapsed ALL patients under the age of 71 years will be registered and randomized to receive prednisone and methotrexate in the pre-phase and thereafter two remission induction courses of alemtuzumab.

In addition to the more classical evaluation methods (morphology, immunophenotyping), the leukemic mass will be studied afterwards from stored blood and bone marrow samples by using the PCR technique for Ig and TCR gene rearrangement as well as for leukemia-specific breakpoint fusion regions at diagnosis and after achievement of first CR.

8 Study population

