11.2.10 Corticosteroid sensitivity

Corticosteroid sensitivity will be determined on day 8 of the pre-phase. Definition of corticosteroid-sensitivity: leukemic blasts $< 1 \times 10^{9}$ /l in the blood.

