14.2 Secondary endpoints

- Toxicity profile related to each treatment step and intervals between treatment steps.
- Event-free survival (i.e. time from registration until no CR on protocol, relapse or death, whichever comes first); Event-free survival for patients without a CR is set at one day.
- Disease-free survival (i.e. time from achievement of CR to date of relapse or death from any cause, whichever occurs first).
- Overall survival measured from time of registration.

15 Data collection

Data will be collected on Case Report Forms (CRF) to document eligibility, safety and efficacy parameters, compliance to treatment schedules and parameters necessary to evaluate the study endpoints. Data collected on the CRF are derived from the protocol and will include at least:

- inclusion and exclusion criteria
- baseline status of patient including medical history and stage of disease
- timing and dosage of protocol treatment
- adverse events
- parameters for response evaluation
- any other parameters necessary to evaluate the study endpoints
- survival status of patient
- reason for end of protocol treatment

Each CRF page will be identified by a pre-printed trial number, and a unique combination of patient study number (assigned at registration), hospital and patient namecode (as documented at registration) to be filled out before completing the form.

The CRF will be completed on site by the local investigator or an authorized staff member. Each page must be dated and signed by the local investigator upon completion. All CRF entries must be based on source documents. The CRF and written instructions for completing the CRF will be provided by the HOVON Data Center.

Copies of the CRF will be kept on site. The original CRF pages must be sent to the HOVON Data Center at the requested time points. How and when to send in forms is described in detail in the CRF header and the CRF instructions.

All data from the CRF will be entered into the study database by the HOVON Data Center.

16 Registration

Eligible patients should be registered and randomized before start of treatment. Patients can be registered at the HOVON Data Center of the Erasmus MC - Daniel den Hoed by phone call: [name] or [contact] Monday through Friday, from 09:00 to 17:00, or via the Internet through TOP (Trial Online Process; https://www.hdc.hovon.nl/top). A logon to TOP can be requested at the HOVON Data Center for participants.

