These design parameters imply that in each treatment arm a maximum of 54 patients who started with induction cycle I will be assessed after induction cycle I for CR rate and severe toxicity, with an interim analysis after the first 24 patients, or as soon as 9 severe toxicities have been reported in the first 24 registered patients, whichever comes first:

- if after the first 24 patients in a treatment arm ≤ 5 CR's (20.8%) are observed, or if ≥ 9 severe toxicities (37.5%) are observed, that arm will be closed to further patient entry with the conclusion that the arm is not enough active or is too toxic, and should not be further investigated. Otherwise patient entry will be extended to 54 patients. However, when 24 patients have been randomized to each treatment arm, a maximum of 4 more patients may be randomized to each treatment arm before the randomization will be put on hold while awaiting the data for and results of the interim analysis.
- If after 54 patients in a treatment arm ≤ 14 CR's (14/54 = 25.9%, 95% CI = 15.0-39.7%) are observed, or if ≥ 18 severe toxicities (18/54 = 33.3%, 95% CI = 21.1-47.5%) are observed, the conclusion will be that the arm is not enough active or is too toxic, and should not be further investigated.
- Otherwise, the trial will conclude that the arm is active and feasible, and warrants further investigation in this patient population.

Since this design applies per treatment arm and does not take into account that the dose in arm B is higher than the dose in arm A, which implies that the true probability of severe toxicity in arm B is not smaller than in arm A and also that the true CR rate in arm B is not smaller than arm A, unless the latter could be explained by a high toxicity rate in arm B, the above stopping rules will be modified in the following way:

- if the observed toxicity rate in arm B is lower than in arm A, the average toxicity rate of both treatment arms will be used in the stopping/decision rules in both arms.
- If the observed CR rate in arm B is lower than in arm A, and this cannot be explained by a high toxicity rate in arm B, the average CR rate of both treatment arms will be used in the stopping/decision rules in both arms.

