Before the interim analysis, CR and toxicity data on induction cycle I will be actively requested for on a monthly basis. For this purpose a short questionnaire will be generated, which should be completed as soon as cycle I has been evaluated, or as soon as it has been decided that cycle I will not be administered at all. In order to overcome dropouts due to ineligibility, 120 patients will be randomized. With an expected accrual rate of 60 patients per year, entry will be completed in about 2-2.5 years, depending on the speed of initiation in each country.

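### Section 17.2 calls a set of eligible patients who started induction intention to treat and applies it to EFS and OS, which run from registration, so failures before cycle I drop out of both

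*Protocol*

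**What the plan says.** Protocol section 17.2 opens with the analysis set: "All randomized patients, eligible and who started the induction treatment will be included in the analysis, according to the intention to treat". It then lists CR rate, severe toxicity rate, and Kaplan-Meier curves for EFS, DFS and OS, with no second population for the survival curves.

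The order of events is set elsewhere:

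- Section 16: "Eligible patients should be registered and randomized before start of treatment".
- Section 7: patients are "registered and randomized to receive prednisone and methotrexate in the pre-phase and thereafter two remission induction courses of alemtuzumab".
- Sections 9.1 and 9.2: the pre-phase occupies days 1 to 7, and the first alemtuzumab dose is on day 8.

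The survival clocks are in section 14.2: "Event-free survival (i.e. time from registration until no CR on protocol, relapse or death, whichever comes first" (with EFS set at one day for patients without a CR), and "Overall survival measured from time of registration".

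Section 17.1 describes the patients behind the decision rule: "in each treatment arm a maximum of 54 patients who started with induction cycle I will be assessed after induction cycle I for CR rate". It also foresees patients who never get that far, since the short questionnaire is due once cycle I has been evaluated or "as soon as it has been decided that cycle I will not be administered at all". The only reason given for randomising 120 patients is ineligibility.

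**The concern.** There are two separate problems.

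**The label.** Two filters act after randomisation: eligibility and having started induction. A set built that way is not an intention-to-treat set. Eligibility is not a formality here, because section 4.1 allows registration and treatment before the diagnosis is confirmed, so ineligibility can come to light after randomisation.

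**The clock and the set do not match.** EFS and OS begin at registration, but a patient enters the analysis only by reaching the start of induction. If that means cycle I, every patient in the OS analysis has by construction survived the pre-phase. For EFS, a patient who never starts cycle I has no CR on protocol and is therefore an event at one day under section 14.2, yet section 17.2 removes that patient from the denominator.

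At stake are the per-arm EFS and OS estimates, which would be too favourable. They are secondary endpoints, but readers will take curves labelled intention to treat and timed from registration as the outlook for everyone randomised.

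**Working it through.** **1. The plan's own figures.** Inputs from section 17.1: CR probabilities 0.20 and 0.40, severe toxicity probabilities 0.40 and 0.20, and error limits of 0.10 each. An arm fails with 5 or fewer CRs or 9 or more severe toxicities among 24, or with 14 or fewer CRs or 18 or more severe toxicities among 54. Exact two-stage binomial probabilities, with CR and toxicity independent:

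- Passing on CR: 0.0881 at 0.20 and 0.9470 at 0.40.
- Passing on toxicity: 0.1015 at 0.40 and 0.9557 at 0.20.
- alpha for CR = 0.0881 x 0.9557 = 0.084.
- alpha for toxicity = 0.9470 x 0.1015 = 0.096.
- Power = 0.9470 x 0.9557 = 0.905.

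All meet the stated limits. For recruitment, 54 / 0.90 = 60 per arm and 2 x 60 = 120, a 10% allowance (6 per arm, 12 in all). No stated design figure is wrong.

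**2. Who is left out.** Section 17.2 does not define induction treatment. Section 7 places the pre-phase before the induction courses. Section 17.1 counts patients who started cycle I and expects some never to receive it. Read together, these make the start of alemtuzumab on day 8 the most natural meaning.

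**3. OS.** Let u be the share of randomised patients left out. After the pre-phase,

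S_all(t) = (1 - u) x S_starters(t) + u x S_excluded(t).

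If the excluded are exactly the patients who die before cycle I, then S_excluded(t) = 0, and with u = e,

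S_all(t) = (1 - e) x S_starters(t).

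**4. EFS.** A non-starter has EFS of one day whether or not the patient survives. From that day on,

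EFS_all(t) = (1 - e) x EFS_starters(t),

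with e now the share of randomised patients who do not start.

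**5. Numbers.** The protocol gives no value for e, so 2% to 10% is an assumed range. The OS levels are illustrative. The CR level of 40% is the design's target value.

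| e | Patients of 120 | OS 40% becomes | OS 50% becomes | EFS just after day 1, starters' CR rate 40%, becomes |
|---|---|---|---|---|
| 2% | 2.4 | 39.2% | 49.0% | 39.2% |
| 5% | 6 | 38.0% | 47.5% | 38.0% |
| 10% | 12 | 36.0% | 45.0% | 36.0% |

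For example, 0.40 x (1 - 0.05) = 0.380. The 10% OS row assumes that the whole recruitment allowance consists of early deaths.

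**6. CR.** At the lowest passing count, 15/54 = 27.8%; over all 60 randomised in the arm, 15/60 = 25.0%. This shows what a sensitivity analysis would display. It is not an error in the decision rule, which section 17.1 openly bases on patients who started cycle I.

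**7. DFS.** It starts at CR, so failures before cycle I never enter it.

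**The case against.** The strongest reply is that the protocol does not say outright that pre-phase deaths are dropped. Day numbering runs on from the pre-phase, and section 11.1 places day 18 within induction cycle I, a count that begins on pre-phase day 1. If the pre-phase counted as induction, deaths on days 1 to 7 would stay in, and only ineligible or wholly untreated patients would be lost. This stands as an ambiguity. Sections 7 and 17.1 weigh against it, and the label would still be wrong because ineligible patients are removed.

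It is also fair that EFS and OS are secondary, that section 17.2 plans estimates rather than a test between arms, and that the go/no-go decision rests on CR and toxicity. This limits the weight of the point without removing it.

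Four stronger readings are tempting, and the documents do not support them:

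- **Guaranteed event-free time to day 8.** A reader might infer this for EFS as well as OS. It cannot hold for EFS, because starters without a CR are also events at one day. The EFS bias is purely one of denominator.
- **A large bias in OS.** A reader might take 36% as the expected figure, or assume a loss of 15% to 20% and reach a gap of 0.40 x 0.15 = 6 to 0.40 x 0.20 = 8 points. Both assume that every excluded patient dies early. Section 17.1 budgets its 10% for ineligibility, and ineligible patients are not by definition early deaths.
- **Bias between arms.** Allocation is given immediately (section 16), so a decision not to start could depend on the arm. Nothing shows that it would. The pre-phase is common, the doses on days 8 and 9 are the same, and the arms first differ on day 10.
- **Randomisation should move to day 8.** That is a design trade-off, not a correction. Ineligibility could still emerge later, and the analysis can be put right without it.

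**Conclusion.** The point holds as an inconsistency in the analysis plan. The set in section 17.2 is a modified set and should not be called intention to treat. Applied to endpoints timed from registration, it makes OS conditional on surviving the pre-phase and drops from EFS patients whom section 14.2 counts as events.

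The direction is clear: if any randomised patient dies before cycle I (OS) or does not start it (EFS), the reported per-arm estimate is too favourable, and the all-randomised value is (1 - e) times it. The size is not known from the documents. At an assumed 2% to 5% the correction to a 40% OS is 0.8 to 2.0 points; the 4.0 points at 10% are a worst case within the planned allowance.

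This rests on reading the start of induction as the start of cycle I and, for the OS factor, on the excluded patients being those who die before cycle I. Non-starters who survive would reduce the OS correction but not the EFS one. Bias between arms is probably small. The decision rule, its cut-offs, the 54 patients per arm and DFS are not affected.

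**What to change.** In section 17.2:

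- Describe the CR and toxicity set as eligible patients who started cycle I, call it a modified set, and remove the intention-to-treat label from it. State that starting induction means receiving the first alemtuzumab dose.
- Analyse EFS and OS on all randomised patients by assigned arm. Non-starters have EFS of one day under the existing no-CR rule; their OS is as observed.
- List all post-randomisation exclusions by arm, with reasons.
- Report CR over all randomised patients as a sensitivity analysis.

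The cost is a wording change, a little more analysis work, follow-up of survival status for non-starters, and slightly less favourable survival figures. Sample size, stopping rules and the time of randomisation stay as they are.

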9.6 Advised treatment off protocol

Note: This phase is not an official part of this protocol and contains only an advise for treatment.

For patients still in complete remission after completion of protocol treatment it is advised to continue with consolidation therapy and (if possible) stem cell transplantation. In patients who did not achieve CR, treatment with high dose Ara-C and mitoxantrone followed by (autologous or) allogeneic stem cell transplantation is advised.

Consolidation therapy may consist of a single course of HAM. The HAM protocol has to start within one month after the last alemtuzumab administration, preferably as soon as the leukocytes and thrombocytes have been recovered.

Agent	Dose/day	Route	Days
Ara-C	3 g/m ² , 3-hr infusion every 12 hrs	i.v.	1, 2, 3, 4
Mitoxantrone	10 mg/m², 30 min infusion	i.v.	3, 4, 5
MTX	15 mg	i.t.	1

In case a suitable stem cell donor is available, an allogeneic stem cell transplantation should be performed as soon as possible.

10 End of protocol treatment

Reasons for going off protocol treatment are:

- 1 Normal completion of protocol treatment
- 2 Progressive disease
- 3 No CR after induction cycle I
- 4 Relapse (bone marrow or extra-medullary)
- 5 Excessive extra-medullary drug toxicity
- 6 Death whatever the cause
- 7 No compliance of the patient (especially refusal to continue treatment)
- 8 Major protocol violation*
- 9 Delay or interruption of treatment, exceeding the limits (see paragraph 9)

* Major protocol violation defined as:

other ALL treatment given than as described in paragraph 9, or not meeting eligibility criteria for inclusion as described in paragraph 8.1.

11 Required clinical evaluations

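### The only analysis set in section 17.2 requires eligibility, so patients given alemtuzumab but judged ineligible are left out of the reported toxicity, and 17.1 describes the decision-rule population differently

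*Protocol*

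**What the plan says.** Section 17.2 of the protocol opens its list of analyses with the population: "All randomized patients, eligible and who started the induction treatment will be included in the analysis, according to the intention to treat". Under that sentence it lists, for both arms, the severe toxicity rate: "The estimated severe toxicity rate (i.e. any side effect or infection of CTCAE grade 4) along with the 95% CI interval will be presented for" […]. It also lists the "tabulation of the incidence of side effects and infections with CTCAE grade 2 or more". No other population is named for either.

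Section 17.1 describes the patients in the two-stage rule in other terms. In each arm "a maximum of 54 patients who started with induction cycle I will be assessed after induction cycle I for CR rate and severe toxicity". The early toxicity trigger applies "as soon as 9 severe toxicities have been reported in the first 24 registered patients". Neither phrase mentions eligibility. The same section then explains the excess over 108 patients: "In order to overcome dropouts due to ineligibility, 120 patients will be randomized".

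Three other places bear on the point:
- Section 4.1 does not require the diagnosis to be confirmed before registration or the start of treatment.
- Section 10 counts as a major protocol violation, and so as a ground for ending protocol treatment, a patient "or not meeting eligibility criteria for inclusion as described in paragraph 8.1".
- Section 13.2 requires adverse events of grade 2 or higher to be reported, with no eligibility condition.

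**The concern.** A safety summary should cover everyone exposed to the drug. Here a dosed patient leaves both the numerator and the denominator of reported toxicity once judged ineligible. That judgement can come after the toxicity is known, in a trial whose protocol describes no blinding. The intention-to-treat label hides this, because a set filtered on eligibility and on having started treatment is not intention to treat.

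The protocol itself makes such patients foreseeable. A diagnosis can be overturned on review after dosing, ineligibility can end treatment already under way, and the sample size includes an allowance for it.

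Severe toxicity is one of two primary endpoints and can close an arm, and section 17.4 installs no data and safety monitoring board. It should therefore be beyond doubt which patients count, both in the reported rate and in the rule. At present 17.1 and 17.2 can be read differently on this.

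**Working it through.** **1. The plan's own design.** Inputs from 17.1: stage 1 has 24 patients per arm, and the arm continues with at least 6 complete remissions (CR) and at most 8 severe toxicities. The full stage has 54, and the arm is accepted with at least 15 CR and at most 17 severe toxicities. CR rates are 20% and 40%, toxicity rates 40% and 20%, and all three error limits 0.10. Each probability of passing is the sum, over stage 1 results that allow continuation, of the binomial probability for 24 patients times the probability that the next 30 keep the total within the final limit. CR and toxicity are taken as independent, and the averaging of arms A and B is ignored.

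- Passing the CR rule: 0.0881 at 20%, 0.9470 at 40%.
- Passing the toxicity rule: 0.1015 at 40%, 0.9557 at 20%.
- Error for CR: 0.0881 × 0.9557 = 0.084. Error for toxicity: 0.1015 × 0.9470 = 0.096. Power: 0.9470 × 0.9557 = 0.905.

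The design meets its limits, and the printed intervals for 14/54 (15.0–39.7%) and 18/54 (21.1–47.5%) reproduce. The fault lies in the analysis set, not in the sample size.

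**2. How many patients could be affected.** 120 − 2 × 54 = 12, which is 12/120 = 10%, or about 6 per arm. The protocol does not say how many of these would have been dosed, so the range is 0 to 6 per arm.

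**3. Effect on the reported rate.** Take an arm with 17 severe toxicities in 54 eligible patients, 31.5%, the highest count that the rule accepts. Add *m* dosed but ineligible patients with *t* severe toxicities: rate = (17 + t)/(54 + m).

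| m | t | All treated | Rate |
|---|---|---|---|
| 6 | 0 | 17/60 | 28.3% |
| 6 | 1 | 18/60 | 30.0% |
| 6 | 2 | 19/60 | 31.7% |
| 6 | 3 | 20/60 | 33.3% |
| 6 | 6 | 23/60 | 38.3% |
| 3 | 0 | 17/57 | 29.8% |
| 3 | 3 | 20/57 | 35.1% |

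The break-even for 6 patients is 6 × 17/54 = 1.9 events. With 0 or 1 event the eligible-only rate is too high; with 2 or more it is too low. In every row *t* events are missing from the reported counts.

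**4. Who counts in the rule.** Set side by side, the protocol gives three descriptions: registered (early trigger, 17.1), started cycle I (24- and 54-patient assessment, 17.1), and eligible and started induction (17.2). The stated reason for randomising 120 fits the third, because it treats ineligible patients as losses to be made good.

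The choice can matter. Assume that 10% of treated patients are ineligible, with severe toxicity of 35% in eligible and 60% in ineligible patients. The mixed rate is 0.9 × 35% + 0.1 × 60% = 37.5%. The probability of passing the toxicity rule is then 0.291 if eligible patients are counted and 0.180 if all treated patients are counted. With 35% in both groups it is 0.291 either way. These toxicity rates are assumptions, not protocol figures.

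**The case against.** A reader might infer that ineligible treated patients drop out of the toxicity stopping rule. Section 17.1 does not say so. The rule under which "≥ 9 severe toxicities (37.5%) are observed, that arm will be closed to further patient entry" is framed for patients who started cycle I, and the early trigger for registered patients. An exclusion there can only be inferred from the reason given for the 120 and from 17.2. What stands is a conflict to be reconciled.

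A reader might also infer that known harm is understated. That needs more grade 4 toxicity in ineligible than in eligible patients. It is plausible for someone who breached the exclusions for active infection or organ dysfunction in 8.1.2, but those criteria are checked against a list at registration (section 16). The clearest documented late route, diagnostic review, has no stated link to toxicity. The protocol gives no figure, and the table shows that the rate can move either way.

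Nor does 20/60 breach a limit. The plan sets a count of 18 at 54 patients and none at 60.

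Some of the 12 may never be exposed, since alemtuzumab starts on day 8 after a week of pre-phase, and 17.1 foresees patients in whom cycle I is not given. Adverse event reporting continues for ineligible patients, so the consequence of 17.2 falls on the reported rates and tables and not on case-by-case surveillance.

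Finally, a statistical analysis plan that is not at hand might define a safety set. But the protocol does not leave the set open. It fixes one and lists the toxicity analyses under it.

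**Conclusion.** The point holds in limited form. As written, 17.2 omits dosed but ineligible patients from the severe toxicity rate and from the toxicity tables, and any events in them are lost from the reported counts. The direction of the effect on the rate is unknown. From 17/54 (31.5%), with the full allowance of 6 dosed ineligible patients, the all-treated rate lies between 28.3% and 38.3%; with none dosed nothing changes. Separately, 17.1 and 17.2 do not agree on the population, and the protocol does not settle whether a grade 4 event in an ineligible treated patient counts towards the 24- and 54-patient limits. This should be corrected, but it does not undermine the design.

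**What to change.** In 17.2, report the severe toxicity rate with its 95% CI and the toxicity tables, per arm, on all randomised patients who received at least one alemtuzumab infusion, whether or not they were eligible. Remove the intention-to-treat label from the eligible-only set. That set can remain for a separately labelled CR rate.

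Reconcile 17.1 and 17.2 so that the 24- and 54-patient rules and the early trigger refer to one stated population, the same for CR and toxicity. Keeping it the same for both matters, because the two-stage design assesses both outcomes in the same patients. Say also how patients who are registered but never start cycle I are handled.

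The cost is a change of wording. The data are already collected, and sample size, boundaries and error rates do not change. The downside is that the reported toxicity rate may be slightly less favourable, and its denominator may differ by a few patients from that of an eligible-only CR rate.
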